### 8.5.3 Analysis of Secondary and Safety Endpoints

#### 8.5.3.1 Analysis of Safety Endpoints

The extent of exposure to avelumab will be characterized by duration (weeks), number of administrations, cumulative dose (mg/kg), dose intensity (mg/kg/week), relative dose intensity (actual dose given/planned dose), number of dose reductions, and number of dose delays.

Safety analyses will be performed on the Safety Analysis Set. The safety endpoints will be tabulated by dose level and cohort, using descriptive statistics.

Safety assessments will be based on review of the incidence of AEs, ADRs, and changes in vital signs, ECGs, body weight, and laboratory values (hematology and serum chemistry).

The on treatment period is defined as the time from the first administration of avelumab to the last administration of avelumab date plus 30 days or the earliest date of subsequent anticancer drug therapy minus 1 day, whichever occurs first.

#### Adverse Events

All AEs will be coded according to the Medical Dictionary for Regulatory Activities. Severity of AEs will be graded using the NCI-CTCAE v4.03 toxicity grading scale.

Treatment-emergent AEs are those events with an onset date occurring during the on-treatment period or if the worsening of an event is during the on-treatment period.

The incidence of TEAEs, regardless of attribution and AEs, defined as possibly related to study treatment will be summarized by Preferred Term and System Organ Class, and described in terms of intensity and relationship to study treatment. Adverse events (serious and nonserious) will be considered TEAEs, except for AEs which started prior to the first administration of avelumab (unless a worsening of the event is recorded after the first administration of avelumab, in which case the event will be considered a TEAE). All premature terminations will be summarized by the primary reason for study withdrawal.

Descriptive statistics will be examined for indications of dose-related ADRs.

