**Planned number of subjects:**

Approximately 21 subjects (up to approximately 24 subjects).

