**Statistical methods:**

The sample size estimated for the study is not based on any statistical assumptions. Rather, it follows the “3 + 3” rule, a well-established methodology for the design of dose-finding studies in oncology.

For the primary endpoints, the number and proportion of subjects experiencing DLTs will be reported by dose level (excluding 10 mg/kg once weekly cohort). Pharmacokinetic parameters will be summarized using descriptive statistics. The point estimate of ORR/median DOR and 95% CIs will be calculated.

The primary analysis, including all endpoints analyses, for study data will be conducted at the time when all subjects complete PK sample collection (including all samples collected if the

treatment discontinued earlier than Week 13). The data cutoff time point for primary analysis is set at Week 13 (Day 85) of the last subject.

The data from primary analysis will be summarized in the Clinical Study Report (CSR).

The final analysis of study data will be conducted after End of Study, which is defined as the last patient complete 90-day Safety Follow-up Phone Call or last patient died, whichever comes first. Additional data from primary analysis up to this cutoff date will be analyzed and presented as an addendum of CSR.

Table 1-1 Schedule of Assessments for Subjects Receiving Avelumab Once Every 2 Weeks

Assessment	Clinical Screening / Baseline Assessments	Treatment Phase 								EOT Visit 	Safety Follow-up 	Long-term Follow-up 	
		≤ Day -14 to Day -1	V1	V2	V3	V4	V5	V6	V7				Until progression
			W1	W3	W5	W7	W9	W11	W13				
			D1	D15	D29	D43	D57	D71	D85				
CCI													
Written informed consent	X												
Inclusion/exclusion criteria	X												
Medical history 	X												
Demographic data	X												
Hepatitis B, hepatitis C, and HIV tests	X												
Full physical examination 	X									X	X		

Assessment	Clinical Screening / Baseline Assessments	Treatment Phase 								EOT Visit 	Safety Follow-up 	Long-term Follow-up 	
		≤ Day -14 to Day -1	V1	V2	V3	V4	V5	V6	V7				Until progression
			W1	W3	W5	W7	W9	W11	W13				
			D1	D15	D29	D43	D57	D71	D85				
Symptom-directed physical exam 		As indicated throughout the Treatment Phase											
Height	X												
Vital signs	X	X	X	X	X	X	X	X	2-weekly	X	X		
Weight	X	X	X	X	X	X	X	X	2-weekly	X	X		

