#### 5.1.1.1 Dose Escalation Design

The dose escalation of this study is based on a modified “3 + 3” cohort design. An initial cohort of 3 Chinese subjects with metastatic or locally advanced solid tumors will receive 3 mg/kg of

avelumab (IMP) once every 2 weeks. Each of these first 3 subjects will be observed for 21 days (DLT observation period). The SMC will review the safety data, including DLTs, and advise on further escalation to the next cohort (10 mg/kg of avelumab once every 2 weeks). As this study represents the introduction of avelumab into a new region, the 3 mg/kg dose has been selected as the starting dose, a minus 1 dose level to avelumab 10 mg/kg, as an extra precaution to further mitigate risks in Chinese subjects (Figure 5-3).

The 10 mg/kg once every 2 weeks cohort will enroll 6 Chinese subjects with metastatic or locally advanced solid tumors. Since more than 1400 subjects have been exposed to avelumab at a dose of 10 mg/kg once every 2 weeks and it has been well tolerated, it is unlikely that there are ethnic differences with respect to avelumab safety and PK; therefore staggered enrolment (3 + 3) will not be used for the 10 mg/kg once every 2 weeks cohort and all 6 slots will be opened at the same time for competitive recruitment.

After completion of 10 mg/kg once every 2 weeks cohort, the avelumab dose will be further escalated up to 20 mg/kg once every 2 weeks to characterize the safety and PK of avelumab at a higher dose level. A staggered “3 + 3” enrolment will be used for the 20 mg/kg avelumab cohort.

Once the safety of avelumab at 20 mg/kg once every 2 weeks have been established and can be regarded as safe (ie, no DLT observed in the first 3 subjects or less than 2 out of the 6 subjects experience a DLT), a new cohort of 10 mg/kg administered once weekly can be immediately initiated to assess safety of already established dose strength with a more frequent dose administration. Six (6) evaluable subjects are planned to be included in this cohort. The DLT assessment is not applicable for the 6 subjects in the 10 mg/kg once weekly cohort. Subjects in this cohort will receive avelumab at 10 mg/kg once weekly for the first 12 weeks. Starting from Week 13, dose frequency will be changed to once every 2 weeks. All 6 slots will be opened at the same time for competitive recruitment.

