### 5.1.2.1.2 Dose Escalation Scheme

Subjects will receive avelumab by IV infusion over 1 hour once every 2 weeks. Dose escalation of avelumab will be performed according to the following dose levels, representing a 3.3 or 2 times increase at each escalation. Each subject will receive a fixed dose of avelumab according to their allocated dose level:

- 3 mg/kg
- 10 mg/kg
- 20 mg/kg

The dose escalation criteria are as follows:

For each dose level, DLTs (as defined in Section 7.4.1.1) will be assessed during the 21 days after administration of avelumab. The criteria for moving from 3 mg/kg to 10 mg/kg of avelumab is if no subject experiences a DLT in the first 3 subjects. No additional 3 subjects will be enrolled. If 1 out of the first 3 subjects in the 3 mg/kg cohort experiences a DLT, this cohort will be expanded to 6 subjects. If  $\geq 2$  out of 3 or 6 subjects in the 3 mg/kg cohort experience a DLT, the study will be placed on hold. See also Section 2.1.

[figure not shown]
In the 10 mg/kg once every 2 weeks cohort, 6 slots will be opened at the same time for competitive enrolment of 6 subjects. If less than 2 out of the 6 subjects in this cohort experience a DLT, the dose of 10 mg/kg will be considered safe in Chinese subjects. If 2 or more subjects experience a DLT, the study will be placed on hold.

After completion of the 10 mg/kg once every 2 weeks cohort, the dose of avelumab will be escalated to 20 mg/kg once every 2 weeks in order to characterize the safety and PK of avelumab at a higher dose level. The criteria for moving from 10 mg/kg to 20 mg/kg of avelumab is if less than 2 out of 6 subjects experience a DLT at the 10 mg/kg dose level (once every 2 weeks cohort). Staggered “3 + 3” enrolment will be used for the 20 mg/kg cohort. If no subject experiences a DLT in the first 3 subjects, the avelumab dose level at 20 mg/kg once every 2 weeks will be regarded as safe in Chinese subjects; the additional 3 subjects will be enrolled to fill up the cohort for PK evaluation, but they will not be subjected to further DLT evaluation.

If 1 subject in the first 3 subjects experiences a DLT (confirmed by SMC only), an additional 3 subjects will be enrolled. If less than 2 out of the 6 subjects experience a DLT, the dose of 20 mg/kg will be considered safe in Chinese subjects. If  $\geq 2$  out of 3 or 6 subjects experience a DLT, the 20 mg/kg cohort will be put on hold (the decision will be made by SMC).

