### 6.5.4 Special Precautions

As a routine precaution, subjects enrolled in this study must be observed for 2 hours after the infusion of avelumab in an area with resuscitation equipment and emergency agents. At all times during study treatment, immediate emergency treatment of an infusion-related reaction or a severe hypersensitivity reaction according to institutional standards must be assured. In order to treat possible anaphylactic reactions, for instance, dexamethasone 10 mg and epinephrine in a 1:1000 dilution or equivalents should always be available along with equipment for assisted ventilation. Please also refer to Section 6.4.

Infusion of avelumab will be stopped in case of  $\geq$  Grade 2 hypersensitivity, inflammatory response, or anaphylactic reaction. The treatment recommendations for infusion-related reactions, according to the NCI are outlined in Section 6.5.5.1. All infusion-related reactions occurring during the infusion of avelumab or within 2 hours after completion of the administration of avelumab should be reported as irAEs.

Investigators should also monitor subjects closely for potential irAEs, which may manifest at the earliest after weeks of treatment. Such events may consist of persistent rash, diarrhea and colitis, autoimmune hepatitis, arthritis, glomerulonephritis, cardiomyopathy, or uveitis and other inflammatory eye conditions.

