6.2 Primary Analysis

The primary analysis, including all endpoints analyses, for study data will be conducted at the time when all subjects complete PK sample collection (including all samples collected if the treatment discontinued earlier than Week 13). The data cut-off time point for primary analysis is set at Week 13 (Day 85) of the last subject.

The data from primary analysis will be summarized in the Clinical Study Report (CSR).

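### In the main CSR, AE percentages are compared across cohorts whose possible follow-up at the single cutoff differs (at least 147 days at 3 mg/kg, 84 on weekly dosing), with no common-window table

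*Protocol*

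**What the plan says.** Protocol 5.1.1.1 and 5.1.2.1.2 open the cohorts in order: 3, 10 and 20 mg/kg every 2 weeks, then 10 mg/kg weekly. Each escalation step waits for a 21-day DLT review. Treatment continues until progression or another withdrawal criterion.

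The primary analysis covers all endpoints and feeds the CSR. SAP 6.2 fixes its timing: "The data cut-off time point for primary analysis is set at Week 13 (Day 85) of the last subject". SAP 9.1 leaves out AEs that start after the cutoff.

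On presentation, protocol 8.5.3.1 states: "The safety endpoints will be tabulated by dose level and cohort, using descriptive statistics". SAP 15.2.1 and 15.2.5 specify numbers and percentages of subjects. SAP 15.2 counts a TEAE from first dose to 30 days after last dose, so the window has no fixed length. The readable AE sections contain no exposure-adjusted rate, time-to-onset analysis or common-window AE table. Under its Adverse Events heading, the protocol adds: "Descriptive statistics will be examined for indications of dose-related ADRs".

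For the weekly cohort, protocol 5.1.1.1 says: "Starting from Week 13, dose frequency will be changed to once every 2 weeks". SAP 13.2 summarises this cohort's duration, cumulative dose, dose intensity and infusions separately for the two dosing phases. No AE table is divided in this way.

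**The concern.** A crude percentage rises with time observed. At the primary cutoff the lowest dose has been observable longest and the most intensive regimen for the shortest time. Equal toxicity would therefore tend to look like less toxicity at the higher intensity, and a real dose trend would be flattened.

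The weekly cohort is the most exposed to this. It was added to assess the safety of more frequent dosing and has no DLT endpoint, so the crude AE tables are its main planned AE comparison in the CSR. Protocol 3.3.1 reports a modest rise in irAEs with higher exposure. Protocol 6.5.4 describes irAEs as events "which may manifest at the earliest after weeks of treatment", so differences in follow-up matter for them.

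A second question is separate. Once weekly-cohort subjects have moved to 2-weekly dosing, their later events fall in the same column as events during weekly dosing, and a reader cannot see which phase they came from.

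**Working it through.** **Cohort sizes.** The plan's total can be reproduced: 3 + 6 + 6 + 6 = 21. The 3 mg/kg cohort may grow ("If 1 out of the first 3 subjects in the 3 mg/kg cohort experiences a DLT, this cohort will be expanded to 6 subjects"), which gives 6 + 6 + 6 + 6 = 24. The synopsis states approximately 21, up to approximately 24.

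**Minimum possible follow-up at the primary cutoff.** Take zero recruitment and review time, no DLT-driven expansion, and a weekly subject as the last subject. Day 85 is 84 days after first dose, and each earlier cohort gains at least 21 days.

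| Cohort | Days | Weeks |
|---|---|---|
| 10 mg/kg weekly | 84 | 12 |
| 20 mg/kg every 2 weeks | 84 + 21 = 105 | 15 |
| 10 mg/kg every 2 weeks | 84 + 42 = 126 | 18 |
| 3 mg/kg every 2 weeks | 84 + 63 = 147 | 21 |

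The range is 147/84 = 1.75-fold.

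**Effect on crude incidence with no true difference.** These inputs are assumptions, not in the documents: a constant first-event hazard h = -ln(0.8)/12 per week (20% by 12 weeks) in every cohort, and exponential time on treatment with median m of 12 or 24 weeks, rate μ = ln 2/m. The tail a = 30/7 weeks is the SAP's 30 days. An event counts if it occurs before the earlier of last dose plus 30 days and the cutoff C. Then

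risk(C) = 1 - exp(-ha) × [ μ/(μ+h) + (h/(μ+h)) × exp(-(μ+h)(C - a)) ].

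| | C = 12 weeks | C = 15 | C = 18 | C = 21 | all windows closed |
|---|---|---|---|---|---|
| m = 12 | 17.7% | 20.2% | 22.3% | 23.9% | 30.1% |
| m = 24 | 18.8% | 22.1% | 25.0% | 27.5% | 43.8% |

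First 3 mg/kg subject against last weekly subject: 23.9/17.7 = 1.35 and 27.5/18.8 = 1.46. With an assumed 40% by 12 weeks, the same formula gives 45.4/35.7 = 1.27 and 51.3/37.7 = 1.36.

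**If weekly dosing truly doubled the hazard in Weeks 1 to 12** (20% or 40% baseline, m = 12 or 24), the risk ratio for weekly against 10 mg/kg every 2 weeks would be:

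- 1.61 to 1.82 in a common 12-week window;
- 1.28 to 1.44 in the crude tables at the primary cutoff, at the minimum gap (12 against 18 weeks);
- 1.18 to 1.40 at the final analysis, with weekly-cohort events pooled across the switch.

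**Final analysis.** Protocol 5.7 and SAP 6.3 place it after the last subject's 90-day call or the last death. The TEAE window ends 30 days after last dose, so every window has closed. The model then gives one incidence for all cohorts (last column).

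**The case against.** Several counter-arguments stand.

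- **The effect is small in subjects.** The 6.2- and 8.7-point differences amount to about 0.2 to 0.3 of a subject in a cohort of 3. Chance dominates, all analysis is descriptive, and the synopsis says: "The sample size estimated for the study is not based on any statistical assumptions".
- **Other safeguards exist.** Escalation rests on a fixed 21-day window. The SMC reviews the weekly cohort after at least 4 weeks of treatment and after 12 weeks of observation. Deaths within 60 days of first dose are tabulated, laboratory values and vital signs are also summarised by visit, and exposure tables and AE listings will show the imbalance. None of these gives a time-aligned AE table.
- **20 mg/kg and weekly may differ little.** The minimum gap is 21 days, and the three additional 20 mg/kg subjects may enrol alongside the weekly cohort.

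A reader might go further in three ways that the documents do not support.

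- **Persistence into the addendum.** By then the windows have closed and administrative follow-up is largely equal. Crude incidence still depends on how long each subject was treated.
- **A head start of about a year, and so roughly a doubling.** A 52-week cutoff in the same model gives up to 40.1/18.8 = 2.1. But the planned period, Q1 2018 to Q4 2019, runs to last subject out and so includes treatment and follow-up. It does not fix the gap at the primary cutoff.
- **Pooling across the switch as an error.** Protocol 3.3.1 defines weekly then 2-weekly dosing as one regimen, so a single column is the legitimate whole-regimen result. A late irAE could stem from the weekly phase. At the primary cutoff the last subject is only at the switch visit, so the point matters mainly at the final analysis.

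**Conclusion.** The concern holds for the primary analysis and main CSR. Sequential opening, one cutoff and crude percentages over a variable window give the lowest dose the longest possible observation and the weekly regimen the shortest. The direction tends to mask dose- or regimen-related toxicity.

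The documents establish only the minimum: 147, 126, 105 and 84 days. Under equal hazards (20% by 12 weeks, median treatment 12 to 24 weeks, both assumed), the first 3 mg/kg subject's expected incidence is about 1.35 to 1.46 times that of the last weekly subject. This compares individual subjects at the extremes, not cohort averages. Longer accrual gaps would widen it, but the documents do not give them.

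The DLT endpoint is not affected. The missing split at the switch is a secondary point about describing timing. With 3 to 6 subjects per cohort, correcting the bias will not make the comparison precise. It is still worth doing because the bias is systematic, its direction is known, and removing it needs no new data.

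**What to change.** In SAP 15.2.1 and 15.2.5, for the primary analysis, add tables of TEAEs, related TEAEs, Grade 3 or higher events, irAEs and IRRs restricted to onset on Days 1 to 84 for all cohorts. Base CSR statements on dose or regimen relation on these tables, and note that irAEs with later onset appear only in the whole-period tables. State also that time on treatment can still differ within the window.

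For the weekly cohort, flag or tabulate events by onset before, or on or after, the actual date of the first 2-weekly dose. A nominal day will not do: the visit window from Week 13 is -3/+1 days, so that dose can fall on Day 82 (85 - 3). Label the split as a description of timing, not as attribution to the 2-weekly regimen.

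Keep the whole-period tables. The cost is SAP wording, a date filter on existing tables, a longer table package and small counts. No new data or subjects are needed.

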## Laboratory Variables

Laboratory results will be classified by grade according to NCI-CTCAE v4.03. The worst on study grades after the first administration of avelumab will be summarized. Shifts in toxicity grading from first treatment to highest grade will be displayed. Results for variables that are not part of NCI-CTCAE will be presented as below, within, or above normal limits. Only subjects with postbaseline laboratory values will be included in these analyses.

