15.3 Clinical Laboratory Evaluation

All laboratory assessments are performed at local laboratories and comply with local requirements.

Laboratory values (including corresponding normal ranges) from local laboratories will be converted into the standard units by data management. The results in standard units will be used for the analyses.

Laboratory results will be classified according to the NCI-CTCAE toxicity grading version 4.03. If toxicities for high and low values of a specific parameter are defined, these toxicities will be analyzed separately for the parameter as “Parameter low” and “Parameter high” (appendix 18.3).

Laboratory results that are not part of the NCI-CTCAE will be presented according to the categories: below normal limits, within normal limits and above normal limits (according to the local laboratories normal ranges).

- **Hematology:** Hematocrit, Hemoglobin, Platelet count, Red blood cells (RBC) count, White Blood Cell Count, Absolute lymphocytes count, Lymphocytes, Absolute Neutrophils count, Neutrophils, Absolute monocyte count, Monocytes, Absolute eosinophil count, Eosinophils, Absolute basophil count, Basophils, RBC morphology, Absolute reticulocytes count, Reticulocytes, Mean corpuscular hemoglobin (MCH), Mean corpuscular volume (MCV), Mean corpuscular hemoglobin concentration (MCHC).
- **Hemostaseology:** Activated partial thromboplastin time (aPTT), Prothrombin time (PT), International Normalized Ratio (INR).
- **Biochemistry:** Albumin, Alkaline phosphatase, Alanine Aminotransferase (ALT), Amylase, Aspartate Aminotransferase (AST), Gamma Glutamyl Transpeptidase (GGT), Blood Urea Nitrogen (BUN), Urea, Calcium, Chloride, Cholesterol, Creatine kinase, Creatinine, C-Reactive Protein (CRP), Glucose, Lactate dehydrogenase (LDH), Lipase, Phosphorus, Magnesium, Potassium, Sodium, Total bilirubin, Protein total, Uric acid, Triglycerides, Hemoglobin A1c.
- **Hormonal tests:** Free Thyroxine (T4), Thyroid-Stimulating Hormone (TSH), Follicle-stimulating hormone.
- **Urinalysis:** pH, Specific gravity, Protein content, Sediment analysis, Albumin, Immunoglobulin G.

NCI-CTCAE grades available:

The laboratory toxicities will be tabulated by the worst on-treatment CTCAE grade or the shift of CTCAE grade from baseline to worst grade during on-treatment period using descriptive statistics (count and percentage). The highest CTCAE grade during the on-treatment period is considered as the worst grade for the summary.

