- The worst grade during the on-treatment period will be summarized considering only patients with post baseline laboratory samples: Laboratory tests by NCI-CTCAE grade (0, 1, 2, 3, 4, and missing).

The shift table will summarize baseline CTCAE grade vs. the worst on-treatment CTCAE grade (grade = 0, 1, 2, 3, 4, missing). The above analyses apply to the following hematology and biochemistry parameters which can be graded per NCI-CTCAE:

- Hematology: Hemoglobin, Lymphocytes, Neutrophils, Platelets, White Blood Cell.

- Biochemistry: Creatinine, Alanine Aminotransferase, Aspartate Aminotransferase, Gamma Glutamyl Transferase, Total Bilirubin, Lipase, Amylase, Albumin, Alkaline Phosphatase, Glucose, Uric Acid, Sodium, Potassium, Calcium, Magnesium, Cholesterol, Creatine kinase, Triglyceride, Phosphorus.

Tables will summarize, separately for hematology and biochemistry parameters, the shift from baseline grade to worst on-treatment grade by parameters and dose level.

NCI-CTCAE grades not available:

The worst on-treatment value for hematology and biochemistry parameters which cannot be graded per NCI-CTCAE will be summarized by parameter according to the local laboratories normal ranges as follows:

- Shift from baseline value (low, normal, high) to above normal during on-treatment period
- Shift from baseline value (low, normal, high) to below normal during on-treatment period.

The above analyses apply to the following hematology and biochemistry parameters which cannot be graded per NCI-CTCAE:

- Hematology: Hematocrit, Red Blood Cells, RBC morphology, Monocytes, Eosinophils, Basophils, Reticulocytes, MCH, MCV, MCHC.
- Biochemistry: Total Protein, Blood Urea Nitrogen, Blood Urea, Chloride, C-Reactive Protein (CRP), Glucose, Lactate dehydrogenase, Hemoglobin A1c.

Quantitative data will also be examined for trends using descriptive statistics (n, missing, mean, SD, median, Q1, Q3, minimum, and maximum) of actual values, absolute changes and percent changes from baseline to each visit over time. This summarization will apply to hematology and chemistry parameters with numeric results assessed at baseline, post-baseline, discontinuation, end of treatment, and safety follow-up visits.

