Listing of clinically significant hematology values and listing of clinically significant biochemistry values will also be provided. Clinically significant values are defined as values with associated NCI-CTCAE grade greater or equal to 3. The following information will be included in those listings:

- Selected dosing information: date of first/last administration
- Laboratory parameter with unit
- Visit of laboratory parameter measurement
- Collection date of laboratory parameter
- Value of laboratory parameter
- Local laboratories normal ranges for laboratory parameter (lower limit of normal and upper limit of normal)

- Normal range indicator for value of the laboratory parameter (Low, Normal, High)
- Associated grade for value of the laboratory parameter according to NCI-CTCAE if applicable.

Other laboratory parameters

The following laboratory parameters collected in the CRF will be presented in specific listing presenting all collected data-fields in the CRF.

- Hemostaseology: Activated partial thromboplastin time (aPTT), Prothrombin time (PT), International Normalized Ratio (INR)
- Hormone: Free T4 and TSH
- Urinalysis: all urinalysis parameters
- Pregnancy test
- Serology

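### SAP Appendix 18.3 gives white blood cell counts below 1.0 x 10^9/L no CTCAE grade, so outputs programmed from it would understate the severest leukopenia on the white blood cell line

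*Protocol*

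**What the plan says.** Protocol 8.5.3.1 (Laboratory Variables) says "Laboratory results will be classified by grade according to NCI-CTCAE v4.03". It makes an exception: "Results for variables that are not part of NCI-CTCAE will be presented as below, within, or above normal limits". SAP 15.3 repeats the grading rule: "Laboratory results will be classified according to the NCI-CTCAE toxicity grading version 4.03". It points to Appendix 18.3 for parameters that have both a low and a high scale.

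WBC does not fall under the exception. SAP 15.3 names the gradable blood counts as "Hematology: Hemoglobin, Lymphocytes, Neutrophils, Platelets, White Blood Cell", and plans worst-grade and baseline-to-worst shift tables with categories 0, 1, 2, 3, 4 and missing. Two further rules in the same section matter here:

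- Worst grade: "The highest CTCAE grade during the on-treatment period is considered as the worst grade for the summary".
- Listing of significant values: "Clinically significant values are defined as values with associated NCI-CTCAE grade greater or equal to 3".

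Appendix 18.3 gives WBC LOW three rows (x 10^9/L): Grade 1, <LLN to 3.0; Grade 2, <3.0 to 2.0; Grade 3, <2.0 to 1.0. The next row is uric acid.

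**The concern.** A grading scale should assign the most severe values to its most severe band. Here the scale stops short. A count below 1.0 x 10^9/L meets none of the printed conditions, and neither SAP 15.3 nor the appendix says what happens to a value that matches no band. Depending on the program's default it could be left missing, be ignored in favour of a milder value from another visit, or fall through to Grade 0.

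Two WBC laboratory outputs are at stake: the worst-grade and shift tables, and the WBC entries in the clinically significant hematology listing. In both, a deeper nadir could be reported as less severe than a shallower one.

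**Working it through.** No sample size or error rate is involved. The check is whether the printed bands cover the range they are meant to grade.

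**Inputs.** The thresholds come from SAP Appendix 18.3, and the categories and rules from SAP 15.3. One assumption is needed: LLN for WBC = 4.0 x 10^9/L. It has no bearing on values below 3.0.

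**Rule applied.** A value x gets grade g if x is below the upper limit of band g and at or above its lower limit. An open band has no lower limit.

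**Step 1: WBC values through the printed scale, then with an open Grade 4 row below 1.0.**

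| WBC (x 10^9/L) | As printed | With the added row |
|---|---|---|
| 3.5 | 1 | 1 |
| 2.5 | 2 | 2 |
| 1.5 | 3 | 3 |
| 1.0 | 3 | 3 |
| 0.99 | none | 4 |
| 0.5 | none | 4 |
| 0.1 | none | 4 |

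Values of 1.0 and above keep their grades. Only values below 1.0 change.

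**Step 2: is this how the table is built elsewhere?** There are 32 directional scales: 12 LOW and 20 HIGH. The LOW scales are albumin, calcium, glucose, hemoglobin, lymphocytes, magnesium, neutrophils, phosphate, platelets, potassium, sodium and WBC. Eleven of the 12 end in an open band; only WBC is closed. All 20 HIGH scales also end open, so 31 of 32 are open-ended. Albumin and hemoglobin LOW also stop at Grade 3, but their last bands are open (<20 g/L and <80 g/L), so no value is lost. A Grade 3 band closed at 1.0 therefore implies a further row.

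**Step 3: consequence under the SAP's own rules.**

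- On-treatment WBC 2.5, 1.5, 0.8: grades 2, 3, none. The worst grade is 3 as printed and 4 with the row added. The 1.5 is listed and the 0.8 is not.
- On-treatment WBC 3.5, 2.5, 0.8: grades 1, 2, none. The worst grade is 2 as printed and 4 with the row added. There is no WBC entry in the listing.
- Only on-treatment WBC 0.8: no grade. The subject goes to missing or Grade 0, depending on the program's default.

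**Step 4: what else would catch the subject?** Neutrophils are part of the white cell count, so WBC < 1.0 implies neutrophils < 1.0 in the same sample. Appendix 18.3 grades neutrophils <1.00 to 0.5 as Grade 3 and <0.50 as Grade 4. Protocol Table 7-1 puts both counts in the same hematology panel. Provided the neutrophil count is reported, the subject is Grade 3 or higher on the neutrophil line.

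**The case against.** **The row may have been lost in reading the PDF.** In the extracted table several last rows sit under the next parameter's label; the platelet Grade 4 row (<25 x 10^9/L), for example, appears under potassium. The missing WBC row would also be a last row. But each displaced row survived and can be recognised by its units, and the labels around WBC (bilirubin, triglycerides, uric acid) are in place. Loss is unlikely but not excluded, so the source PDF should be checked first.

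**SAP 15.3 names CTCAE v4.03 itself.** A programmer who works from that source, which SAP section 17 cites, would not be misled. This stands. A reader might infer that the WBC Grade 4 column is empty whatever is done; the documents support that only if the appendix is what gets programmed. That is a realistic route, since the SAP's modification history shows the appendix was added on purpose in Final 2.0.

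**The subject does not disappear.** A reader might infer that a subject with WBC below 1.0 drops out of all Grade 3 or higher outputs. That does not follow: neutrophils would normally flag the same sample, the by-visit statistics in SAP 15.3 include the minimum, and Protocol 8.5.1 lists all recorded data. Adverse event tables use investigator grading, and DLTs are captured from the adverse event form (SAP 15.1).

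**The protocol is not at fault.** A reader might also take the quoted protocol sentence as the error, or as requiring a grade for every laboratory result. It does neither, because variables outside CTCAE are exempt. The conflict is between SAP Appendix 18.3 and SAP 15.3.

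**Cases will be few.** Entry requires WBC >= 3 and neutrophils >= 1.5 x 10^9/L (Protocol 5.3.1), chemotherapy is prohibited on study (6.5.2), and about 21 subjects are planned. This stands.

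**Conclusion.** The point holds as a specification error in SAP Appendix 18.3. WBC is declared gradable on 0 to 4, but its LOW scale leaves everything below 1.0 x 10^9/L ungraded. Outputs programmed from the appendix would understate or omit such a value in the WBC worst-grade and shift tables and in the WBC part of the Grade 3 or higher listing.

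The practical effect is small and confined to the WBC line. The documents give no frequency, and it is probably low. If one case occurred, it would be 1/6 = 17% of a cohort of six or 1/3 = 33% of a cohort of three on that line. That is the weight of a single case, not an expected effect. No primary endpoint or escalation decision depends on it.

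The conclusion assumes that the row is absent from the source PDF and that the appendix drives the program. It rests on the SAP's own 0 to 4 categories and on the pattern of the other 31 scales. It is worth correcting because the WBC tables would otherwise contradict the neutrophil tables for the same subject.

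**What to change.** 1. Look at Appendix 18.3 in the source PDF. If the row is there, the point closes.
2. If it is not, add to White Blood Cell, LOW: Grade 4, <1.0 x 10^9/L, confirming the label against the CTCAE version that the SAP cites.
3. Add a programming check on the table itself: within each defined directional scale, the bands are contiguous in value, do not overlap, and are open at the most severe grade.

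The check in step 3 would also catch the AST Grade 4 row, printed as >20 IU/L although Grade 3 is >5 to 20 x ULN. Since 5 x 4 = 20, any ULN of 4 IU/L or more puts the whole Grade 3 band inside the printed Grade 4 row.

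A broader check, that every value outside the normal range has exactly one grade, should not be used because it would fail on valid data. WBC HIGH has only a row above 100.0, so a WBC of 12 that exceeds the ULN correctly has no grade.

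The cost is one table row, the matching line in the grading program and a short check. No new data are needed, and grades for WBC of 1.0 and above do not change.
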